Investigator	A person, with the appropriate qualifications, responsible for the conduct of the registry at a study site.
Lack of Efficacy/Lack of Effect	Lack of efficacy/effect is the failure of expected pharmacologic action or therapeutic benefit.
MTP	Patients who have received at least one ED but less than or equal to 150 documented prior Factor IX EDs (≤ 150 EDs).
On-demand treatment	Treatment of hemorrhages, as needed, by administering an unscheduled bolus infusion of BeneFIX to stop bleeding and control hemostasis.
Preventive treatment	Factor IX replacement therapy given before an event that could increase the risk of bleeding (e.g. surgery or exercise).
Prophylaxis	Factor IX replacement therapy administered at a routine interval such as every other day, for a prolonged period of time, to prevent occurrence of spontaneous bleeding episodes.
Prothrombin Complex Concentrates	Produced from the cryoprecipitate supernatant of plasma pools after removal of antithrombin and factor XI. Depending on the processing technique, PCCs may contain clotting factors II, IX, X and sometimes VII. To prevent activation of these factors, most PCC contain heparin. PCC may also contain the natural coagulation inhibitors protein C and protein S.
PTP	Patients who have received more than 100 documented prior Factor IX EDs (>150 EDs).
PUP	Patients who have not received any Factor IX products
Registry start date	Date the first registry subject provides informed consent.
Registry end date	Date of last contact with the last subject on the registry.
Regulation	The term regulation refers to all applicable regulations, laws, and guidelines. The regulations may be international, national, or local and may include but are not limited to the Code of Federal Regulations (United States); the European Clinical Trials Directive; the

	International Conference on Harmonisation (ICH) Guideline for Good Clinical Practice; and the World Medical Association Declaration of Helsinki: Ethical Principles for Medical Research Involving Human Subjects.
Treatment Period	Day 0 until study completion/withdrawal

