7. RESEARCH METHODS

7.1. Study design

This is a non-interventional, voluntary prospective registry study conducted in major hemophilia treatment centers in China. The registry will enroll Chinese patients with Hemophilia B of all severities. Patients will undergo a screening review prior to enrollment. Enrolled subjects will be treated with intravenous infusions of BeneFIX at a dose and frequency prescribed by the subject's treating physician in accordance with the BeneFIX label and will be adjusted solely according to medical and therapeutic necessity. The registry study will capture observations that will be used for evaluating recombinant FIX replacement product safety, including: subject demographics, medical history, hemophilia history and medications. Safety assessments, treatment data and any laboratory-based FIX inhibitor determinations will be collected at all visits. It is recommended that all subjects in this registry study will be followed for a minimum of 6 months and participation in this registry study will conclude after 12 months.

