7.8. Data analysis

Detailed methodology for summary and statistical analyses of data collected in this study will be documented in a Statistical Analysis Plan (SAP), which will be dated, filed and maintained by the sponsor. The SAP may modify the plans outlined in the protocol; any major modifications of primary endpoint definitions or their analyses would be reflected in a protocol amendment.

A statistical sample size calculation will not be performed for this study. Because all eligible and willing-to-participate subjects will be enrolled in the study and no statistical hypotheses are tested.

All safety and efficacy analyses, except the analysis for Annualized Bleeding Rates (ABR), will be performed on all subjects who receive at least one dose of BeneFIX. ABR analysis will be performed on subjects who participated in prophylaxis period for at least 6 months.

The primary safety outcomes to be reported will be development of clinically significant FIX inhibitors, FIX hypersensitivity allergic reactions, thrombogenicity, lack of effect and red cell agglutination.

Secondary safety outcomes include the frequency of adverse events and serious adverse events, etc.

Secondary efficacy outcomes will be:

- Annualized bleeding rates (ABR) in subjects receiving treatment with BeneFIX,
- The responses to all on-demand treatment with BeneFIX for all bleeds (4 point scale of assessment),
- Number of BeneFIX infusions to treat each new bleed,
- Number of spontaneous/non traumatic breakthrough bleeds within 48 hours of a prophylaxis dose of BeneFIX.

The efficacy results of this study will be presented using descriptive statistics. The following descriptive statistics will be used:

- For numeric endpoints: sample size, mean, standard deviation, median, minimum and maximum;
- For categorical endpoints: count and percentage.

Safety data will be tabulated and listed according to Pfizer's standard reporting algorithms. The reasons for discontinuation of BeneFIX therapy will be described.

Subgroup analysis will be done by several sub-populations.

Additional details of the analysis will be provided in the statistical analysis plan and/or the clinical study report. This information may include details of missing and, if applicable, unused and spurious data. Deviations from the statistical plan will be reported in the clinical study report.

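### Breakthrough bleeds within 48 hours of a prophylaxis dose are stated as a count with no denominator, over all treated subjects, so the figure mixes protection with prophylaxis exposure

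*Protocol*

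**What the plan says.** The protocol lists four efficacy outcomes in the same terms in the abstract, section 7.4.2 and section 7.8. The last is "Number of spontaneous/non traumatic breakthrough bleeds within 48 hours of a prophylaxis dose of BeneFIX". None of the three places divides it by infusions, subjects or time.

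Section 7.8 then fixes two further things:

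- **Summary statistics.** "For numeric endpoints: sample size, mean, standard deviation, median, minimum and maximum".
- **Analysis set.** "All safety and efficacy analyses, except the analysis for Annualized Bleeding Rates (ABR), will be performed on all subjects who receive at least one dose". ABR alone is treated differently: "ABR analysis will be performed on subjects who participated in prophylaxis period for at least 6 months".

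Exposure to prophylaxis is not held constant. Under section 7.1, subjects are treated "at a dose and frequency prescribed by the subject's treating physician in accordance with the BeneFIX label". Section 1 defines prophylaxis as "Factor IX replacement therapy administered at a routine interval such as every other day", which is an example and not a fixed schedule. Section 7.1 recommends that subjects be "followed for a minimum of 6 months and participation in this registry study will conclude after 12 months", and section 8.2 allows withdrawal at any time. Section 7.4.1 records whether a subject is on prophylaxis or on-demand treatment at enrolment, so both kinds of subject enter the registry.

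**The concern.** A bleed can count only if it falls within 48 hours after a prophylaxis dose. More doses, or a longer time on prophylaxis, give more opportunity for a counted bleed at the same level of protection. A subject with sparse dosing or early withdrawal has less opportunity, and a subject with no prophylaxis dose has none. A mean or median count over all treated subjects therefore depends on three things at once: how well prophylaxis protects, how much was given and for how long, and what share of the registry received any.

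The protocol deals with observation time for ABR, which is annualised and limited to subjects with at least 6 months of prophylaxis. Neither safeguard is stated for this outcome. ABR does not replace it, because ABR does not isolate bleeds shortly after a dose. Section 7.8 also plans subgroup analyses. Subgroups that differ in regimen, follow-up or share on prophylaxis would differ on this count even if protection were the same.

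**Working it through.** The protocol gives no expected count for this outcome, so there is no figure to reproduce. The calculation below shows how the stated metric behaves.

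**Inputs from the protocol:** the 48-hour window (2 days); every other day as the example prophylaxis interval (section 1); the 6- and 12-month marks (section 7.1).

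**Assumptions, not in the protocol:** a bleed rate *r* = 4 per year spent inside windows, constant within them; dosing intervals of 3.5 and 7 days; a 3-month early withdrawal; the shares of subjects on prophylaxis.

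**Formula.** Expected count = *r* × min(1, 2/interval in days) × years on prophylaxis. Infusions = days on prophylaxis / interval.

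| Interval | Time | Window-years | Expected count | Infusions | Per 100 infusions |
|---|---|---|---|---|---|
| 2 days | 12 months | 1.000 | 4.00 | 182.5 | 2.19 |
| 2 days | 6 months | 0.500 | 2.00 | 91.3 | 2.19 |
| 3.5 days | 12 months | 0.571 | 2.29 | 104.3 | 2.19 |
| 3.5 days | 6 months | 0.286 | 1.14 | 52.1 | 2.19 |
| 7 days | 12 months | 0.286 | 1.14 | 52.1 | 2.19 |
| 7 days | 6 months | 0.143 | 0.57 | 26.1 | 2.19 |

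**Spread.** 4.00 / 0.57 = 7. This is 3.5-fold from the interval (4.00 / 1.14) times 2-fold from follow-up. With 3 months of weekly dosing the count is 4 × 2/7 × 0.25 = 0.29, a 14-fold spread.

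**Dependence on the assumed rate.** The counts are proportional to *r*, running from 0.143*r* to *r* over the six rows: 0.29 to 2.0 at *r* = 2, and 1.14 to 8.0 at *r* = 8. The ratio of 7 does not depend on *r*. It does depend on the regimens chosen.

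**The ordering can reverse.** Over 12 months, weekly dosing at 6 per window-year gives 6 × 2/7 = 1.71 counted bleeds. Every-other-day dosing at 3 per window-year gives 3.0. The subject with twice the rate inside the windows has the lower count. Per 100 infusions the order is restored: 6 × 2/365 × 100 = 3.29 against 3 × 2/365 × 100 = 1.64.

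**Structural zeros.** If subjects with a prophylaxis dose average 4.0 and make up 75%, 50% or 25% of all treated subjects, the mean over everyone is 3.0, 2.0 or 1.0. If fewer than half have a prophylaxis dose, the median is 0 whatever the protection.

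**Limit of the per-infusion rate.** It is level only when windows do not overlap, that is, for intervals of 2 days or more. With a hypothetical daily schedule, 365 infusions still cover only 365 days, so 4.0 / 365 × 100 = 1.10 per 100 infusions at the same protection. A rate per unit of time inside the windows, with overlapping time counted once, remains 4.0 per window-year in every case.

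**The case against.** The strongest reply is that this is detail for the SAP. Section 7.8 leaves detailed methodology to the SAP, lets the SAP modify the protocol's plans, and reserves an amendment for major changes to primary endpoint definitions or analyses. This outcome is secondary, so a denominator could be set there without an amendment. That stands, and it means the protocol does not establish that only a raw count will be reported. It does not remove the point: section 7.8 is not silent but names a metric, its summary statistics and its analysis set. Followed as written, these give the figure described above.

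Three stronger readings are tempting but not supported:

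- **That the count is fixed as per subject.** No unit is stated. The mean and standard deviation suggest it, but they belong to a general list for all numeric endpoints. A pooled total would have the same weakness.
- **That the count shows exposure and not protection.** It is rate times exposure, so it carries both. Among subjects with similar regimens and follow-up it is still informative.
- **That a 7-fold distortion is to be expected.** That figure compares assumed extremes. The actual mix of regimens is unknown, and the protocol's only example interval is every other day.

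It is also fair to say that the impact is small. This is one of four secondary efficacy outcomes, no hypothesis is tested, the primary outcomes are safety events, and ABR gives a time-adjusted bleeding measure. No subgroup comparison on this particular outcome is specified.

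**Conclusion.** The point holds in a limited form. As stated, the outcome has no denominator and is assigned to all treated subjects, while dosing frequency, follow-up and treatment mode all vary. The resulting count mixes protection with prophylaxis exposure and is diluted by subjects who cannot have the event, so it should not be compared across regimens, durations or subgroups.

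That conclusion follows from the protocol's text. The size does not: 0.57 to 4.0 expected bleeds at identical protection rests on the assumed rate, regimens and durations, and the dilution from 4.0 to between 3.0 and 1.0 rests on assumed shares on prophylaxis. A reader might infer that the registry's efficacy assessment as a whole is compromised. The protocol does not support that: the issue is confined to one secondary descriptive outcome, and the data to repair it are collected. In a descriptive registry, though, the reported number is the result, so it is worth correcting.

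**What to change.** Reword the outcome in the abstract, section 7.4.2 and section 7.8, and carry it into the SAP:

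1. Restrict this outcome to subjects with at least one prophylaxis infusion during the registry. Do not select on treatment mode at enrolment, since a regimen may change.
2. Report total qualifying bleeds over total prophylaxis infusions, per 100 infusions.
3. Beside it, report a rate per unit of time inside the 48-hour windows, counting overlapping time once and ending at the close of follow-up. This remains valid if windows overlap.
4. Report the proportion of these subjects with at least one such bleed.
5. Show the raw count only next to its number of prophylaxis infusions.

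Cost: a free improvement. Section 7.4.2 already collects infusions, exposure days and bleeds in the diaries. The outcome as worded already requires prophylaxis doses to be identified and timed, so the denominators need no new data.

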7.9. Quality control

The sponsor performs quality control and assurance checks on all clinical studies that it sponsors. Before enrolling any subjects in this study, sponsor personnel and the investigator review the protocol, the investigator's brochure, the CRFs and instructions for their completion, the procedure for obtaining informed consent, and the procedure for reporting AEs and SAEs. A qualified representative of the sponsor will monitor the conduct of the study. During these site visits, information recorded in the CRFs is verified against source documents.

7.10. Other aspects

Not applicable

8. PROTECTION OF HUMAN SUBJECTS

8.1 Patient Information and Consent

All parties will ensure protection of patient personal data and will not include patient names on any sponsor forms, reports, publications, or in any other disclosures, except where required by laws. In case of data transfer, Pfizer will maintain high standards of confidentiality and protection of patient personal data.

The informed consent form must be in compliance with ICH GCP, local regulatory requirements, and legal requirements.

The informed consent form used in this study, and any changes made during the course of the study, must be prospectively approved by both the IRB/IEC and Pfizer before use.

The investigator must ensure that each study patient, or his/her legally acceptable representative, is fully informed about the nature and objectives of the study and possible risks associated with participation. The investigator, or a person designated by the investigator, will obtain written informed consent from each patient or the patient's legally acceptable representative before any study-specific activity is performed. The investigator will retain the original of each patient's signed consent form.

8.2 Patient withdrawal

Patients may withdraw from the study at any time at their own request, or they may be withdrawn at any time at the discretion of the investigator or sponsor for safety, behavioral, or administrative reasons. In any circumstance, every effort should be made to document patient outcome, if possible. The investigator should inquire about the reason for withdrawal and follow-up with the patient regarding any unresolved adverse events.

For patients that are withdrawn from the study prior to the 12 month visit, the treatment and safety data are to be collected at that visit and it is recommended to collect a FIX Inhibitor sample that is analyzed at the local laboratory. A Follow-up Call is to be conducted at least 28 calendar (+10 days) after the Final/Early Termination visit in order to collect information on the occurrence of adverse events and concomitant medications. If the patient withdraws from the study, and also withdraws consent for disclosure of future information, no further evaluations should be performed, and no additional data should be collected. The sponsor may retain and continue to use any data collected before such withdrawal of consent.

8.3 Institutional Review Board (IRB)/Independent Ethics Committee (IEC)

It is the responsibility of the investigator to have prospective approval of the study protocol, protocol amendments, and informed consent forms, and other relevant documents, (e.g., recruitment advertisements), if applicable, from the IRB/IEC. All correspondence with the IRB/IEC should be retained in the Investigator File. Copies of IRB/IEC approvals should be forwarded to Pfizer.

8.4 Ethical Conduct of the Study

The study will be conducted in accordance with legal and regulatory requirements, as well as with scientific purpose, value and rigor and follow generally accepted research practices described in *Good Pharmacoepidemiology Practices* (GPP) issued by the International Society for Pharmacoepidemiology (ISPE), *Good Epidemiological Practice* (GEP) guidelines issued by the International Epidemiological Association (IEA), *Good Outcomes Research Practices* issued by the International Society for Pharmacoeconomics and Outcomes Research (ISPOR), *International Ethical Guidelines for Epidemiological Research* issued by the Council for International Organizations of Medical Sciences (CIOMS), European Medicines Agency (EMA) European Network of Centres for Pharmacoepidemiology and Pharmacovigilance (ENCePP) *Guide on Methodological Standards in Pharmacoepidemiology*, and *FDA Guidance for Industry: Good Pharmacovigilance and Pharmacoepidemiologic Assessment*, *FDA Draft Guidance for Industry and FDA Staff: Best Practices for Conducting and Reporting of Pharmacoepidemiologic Safety Studies Using Electronic Healthcare Data Sets*, *Guidance for Industry: Patient-Reported Outcome Measures: Use in Medical Product Development to Support Labeling Claims and/or equivalent*.

9 MANAGEMENT AND REPORTING OF ADVERSE EVENTS/ADVERSE REACTIONS

9.1 Adverse Event Reporting

9.1.1 Adverse Events

All observed or volunteered adverse events regardless of treatment group (if applicable) or suspected causal relationship to BeneFIX will be recorded on the adverse event page(s) of the case report form (CRF) as follows.

For all adverse events, the investigator must pursue and obtain information adequate both to determine the outcome of the adverse event and to assess whether it meets the criteria for classification as a serious adverse event (see section "Serious Adverse Events") requiring immediate notification to Pfizer or a Pfizer-designated representative. For all adverse events, sufficient information should be obtained by the investigator to determine the causality of the adverse event. The investigator is required to assess causality. For adverse events with a causal relationship to BeneFIX follow-up by the investigator is required until the event or its sequelae resolve or stabilize at a level acceptable to the investigator, and Pfizer concurs with that assessment.

9.1.2 Reporting Period

For non-serious and serious adverse events, the reporting period to Pfizer or its designated representative begins from the time of the patient's first dosing in the observational period as per study design through and including 28 calendar days after the last administration of the study drug within the observational period. If the investigator becomes aware of a SAE that is considered related to study drug occurring at any other time after completion of the study, the SAE is also reportable.

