7.2.2 Approximate Duration of Subject Participation

The frequency of the registry study visits may be conducted following the local standard of care, however, the sponsor recommends that registry study visits be conducted at a minimum of 6 months after the enrollment baseline visit (Day 0) with an additional visit at 12 months after Day 0. A Follow-up Call is to be conducted at least 28 calendar (+10 days) after the Final/Early Termination visit in order to collect information on the occurrence of adverse events and concomitant medications.

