7.4.3 Safety Data Collection (Day 0 to 12 months/Early Withdrawal)

Safety data collected throughout the treatment period (Day 0 to 12 months/Early Withdrawal) will consist of:

- All AE and SAE data, including product-related medically important adverse events (inhibitor development, FIX hypersensitivity allergic reactions, thrombogenicity, lack of effect and red cell agglutination,). This data will be reported on the appropriate CRF and AEM forms during treatment with BeneFIX.

- Laboratory results determining the presence of FIX inhibitor antibodies by the Bethesda assay or Nijmegen modification of the Bethesda assay are recommended to be collected for subjects at all study visits.
- Changes in concomitant diseases or medicinal therapy
 1. Medicinal concomitant therapy
- FIX activity and recovery values, if available and assessed at routine clinic visits.

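### Section 9.1.2 ends adverse-event reporting 28 days after the last BeneFIX dose, contradicting the Day 0 to 12 months collection and the later follow-up call; for on-demand patients it can close before the final visit

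*Protocol*

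**What the plan says.** The protocol gives three different ends for adverse-event capture, and two starts.

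- **Section 9.1.2 (Reporting Period).** For serious and non-serious events, reporting to the sponsor "begins from the time of the patient's first dosing in the observational period as per study design" and runs "through and including 28 calendar days after the last administration of the study drug within the observational period". A further clause makes later events reportable, but only serious ones considered related to study drug, and only after the study is complete.
- **Section 7.4.3 (Safety Data Collection).** "Safety data collected throughout the treatment period (Day 0 to 12 months/Early Withdrawal) will consist of" all adverse-event data, inhibitor results and other items. The section adds: "This data will be reported on the appropriate CRF and AEM forms during treatment with BeneFIX". The definitions table in section 1 sets the Treatment Period as "Day 0 until study completion/withdrawal", with no link to dosing.
- **Sections 7.2.2, 7.3 and 8.2.** "A Follow-up Call is to be conducted at least 28 calendar (+10 days) after the Final/Early Termination visit", to collect adverse events and concomitant medications.

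The sponsor recommends a visit at a minimum of 6 months, "with an additional visit at 12 months after Day 0" (section 7.2.2). Inhibitor results "are recommended to be collected for subjects at all study visits" (section 7.4.3). Section 9.2 gives inhibitor development and the other four medically important events the same reporting requirements as serious adverse events.

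**The concern.** A window tied to the last dose works when dosing is continuous. The registry also takes on-demand patients, whose infusions are by definition unscheduled, and patients may stop BeneFIX during the year. For either group the 9.1.2 window can run out months before the final visit, while sections 7.4.3 and 7.2.2 still expect adverse events to be gathered.

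The primary safety outcomes in section 7.8 include clinically significant inhibitors. Section 1 defines these as a local positive test plus clinical observations within 4 weeks before or after it: at least two events of reduced efficacy, or a need for alternate haemostatic products or for more intensive dosing. If a positive result comes from a final visit outside the 9.1.2 window, a site following 9.1.2 has no stated duty to report it as a medically important event, or to report the events around it. A site following 7.4.3 would do both. Capture of a primary event would then depend on which section a site reads and, indirectly, on the patient's regimen. No analysis plan can later recover events that sites did not report.

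**Working it through.** The protocol states no figure for this point, so there is nothing to reproduce. The check is date arithmetic, followed by a sensitivity calculation on an assumed infusion rate.

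**Inputs from the protocol.** Window end = last-dose day + 28 (9.1.2). Final visit = 12 months, taken as day 365 (7.2.2). Follow-up call = 28 to 38 days after the final visit, reading the +10 days as an allowance: days 393 to 403. Clinical observations for the inhibitor definition: 4 weeks either side of the positive test (section 1).

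**Step 1: when the window closes too early.** It closes before the final visit if last-dose day + 28 < 365, that is, if the last dose falls before day 337.

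| Last dose (day) | Window closes (day) | Days uncovered before day 365 | Days from closure to call |
|---|---|---|---|
| 90 | 118 | 247 | 275 to 285 |
| 180 | 208 | 157 | 185 to 195 |
| 270 | 298 | 67 | 95 to 105 |
| 337 | 365 | 0 | 28 to 38 |

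A patient dosed weekly up to the final visit has a window that ends 21 to 28 days after it. The gap before the final visit therefore concerns on-demand and discontinued patients.

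**Step 2: the inhibitor definition.** For a positive test on day 365, the clinical observations fall between day 337 (365 − 28) and day 393 (365 + 28). If the last dose is before day 309 (337 − 28), the 9.1.2 window closes before that whole interval begins.

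**Step 3: the late-event clause.** It applies after study completion. Read literally, it covers nothing between last dose + 28 days and completion, and no non-serious event at any time.

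**Step 4: how many patients (assumption).** The protocol gives no bleed or infusion frequency. Suppose on-demand treatment episodes follow a Poisson process at λ per year, each counted as one dosing date. Then

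P(window closes before day 365) = P(no episode in the last 28 days) = exp(−λ × 28/365).

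| λ per year | λ × 28/365 | Share affected |
|---|---|---|
| 3 | 0.230 | 79% |
| 6 | 0.460 | 63% |
| 12 | 0.921 | 40% |
| 24 | 1.841 | 16% |
| 52 | 3.989 | 2% |

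The share is one half at λ = ln 2 × 365/28 ≈ 9 a year. With r = λ/365, the mean number of uncovered days before the final visit, averaged over all on-demand patients, is [exp(−28r) − exp(−365r)]/r: 38.2 days at 6 a year, 12.1 at 12 and 2.4 at 24.

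**Step 5: after the fix.** With the window running to the follow-up call, no days before the final visit are uncovered at any infusion rate.

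**The case against.** The strongest reply is that 9.1.2 governs reporting to the sponsor, whereas collection is set elsewhere. Section 9.1.1 has all observed or volunteered adverse events recorded on the case report form, section 7.4.3 collects to 12 months, and the call then follows in sequence. On this view only one sentence is out of line. That narrows the consequence but does not remove the conflict: sites are given a closing date for reporting that differs from the other sections, and medically important events carry reporting duties, not just data entry. The phrase in 7.4.3 about reporting during treatment does not settle it, because the defined Treatment Period runs to study completion.

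Four stronger readings might be inferred, and the documents do not support them.

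- **That the window often closes early.** No infusion frequency is given, and the share above runs from 79% to 2% with the assumed rate. The model leaves out preventive infusions and repeat infusions within an episode, both of which would lower it. It gives the chance that the window closes, not that an event is missed.
- **That late inhibitors are lost.** Inhibitor results are a separate collected item at visits, with no link to the last dose. Testing and visit timing are themselves only recommended.
- **That on-demand patients would look safer.** No comparison by regimen is stated, no hypothesis is tested, and no number of missed events can be derived. Hypersensitivity to BeneFIX, lack of effect and red-cell agglutination are largely tied to infusions, so a dose-based window would lose few of them. A patient more than 28 days past the last dose also has little scope for showing reduced efficacy of BeneFIX at that time, although a need for alternate products remains possible.
- **That any late positive should count as the primary outcome.** Sections 1 and 7.8 require clinical significance; a local positive alone is not enough.

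**Conclusion.** Wrong as written. The reporting period in 9.1.2 contradicts the collection period in 7.4.3, the Treatment Period in section 1 and the follow-up call in 7.2.2, 7.3 and 8.2. The starts differ as well: first dosing against Day 0. These contradictions rest on the text alone.

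That the window can close before the final visit also follows from the text, given unscheduled on-demand dosing and a final visit near day 365. How frequently it does so is not established; the shares depend on the assumed rate and on the Poisson model.

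The consequence is limited to four things: reporting of a late positive as a medically important event, capture of the clinical events within 4 weeks of it that the primary definition needs, capture of other late adverse events, and consistency between sites and regimens. In a registry whose primary objective is these events, that justifies correcting the text.

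**What to change.** Reconcile section 1 (Treatment Period) and sections 7.2.2, 7.3, 7.4.3, 8.2 and 9.1.2 to a single adverse-event window.

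- In 9.1.2, define it as running from the first dose on or after Day 0 through the later of (a) the follow-up call after the Final/Early Termination visit and (b) 28 days after the last dose. Keep the clause on related serious events after completion.
- In 7.4.3, refer to that window and remove the ambiguity about reporting during treatment.
- State that a positive inhibitor result on any study-visit sample is reportable as a medically important event whatever the time since the last dose, and that its classification as clinically significant still follows section 1.

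The cost is a few sentences and some extra adverse-event records in on-demand or discontinued patients. The follow-up call is already planned, so no visit or contact is added.
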